3.5 Withdrawal of Subjects

The participant will remain free to withdraw at any time from the trial without giving reasons and without prejudicing his/her further treatment and will be provided with a contact point where he/she may obtain further information about the study and where they can receive further needed care. Patient's withdrawn and needing clinical care will be referred for a visit to *Glasgow Blood Pressure Clinic at QEUH*. Referrals to *Glasgow Blood Pressure Clinic* will be a written letter and participants will be directed to NHSGGC [name]/[name] led clinic.

Where a participant is required to re-consent or new information is required to be provided to a participant, the PI will ensure this is done in a timely manner.

The investigator can withdraw participants from the study in the event of inter-current illness or identification of a secondary cause for hypertension. Participants who withdraw from the study will be replaced with additional participants until 120 participants/arm have attended the final study visit.

***Verbal consent will be obtained from the participants prior to eligibility screening and/or referral to NHSGGC to QEUH General Medicine/Hypertension Clinic*

****Participants who are either ineligible or no longer wish to take part in the study will be asked if they would like a referral to QEUH General Medicine/Hypertension Clinic for further diagnosis and treatment, and they will be provided with the contact details for QEUH General Medicine/Hypertension Clinic. Referrals to QEUH Glasgow Hypertension Clinic will be a written letter and participants will be directed to NHSGGC [name]/[name] led clinic.*

4. Study Schedule and Trial procedures

NB:

- *Please refer to the InflammaTENSION Manual of Study Operations for an in-depth detail of the study procedures*
- *Please refer to Table 1: Study Schedule*

4.1 Recruitment

Once identified and consented as described in section 3.4 the study visit activities can commence.

4.3 Study Visit Information

- **Location:** All study visits will take place at Glasgow Clinical Research Facility 5th Floor, Neurosciences Building Queen Elizabeth University Hospital Campus [name]
- **Number of Study Visits:** All participants will attend a baseline study visit and visit 1 -either separately or combined depending on the participants wishes and availability of ABPM within past 3 months.
- An additional telephone contact and verification will be performed 3.5months +/- 2 weeks after final study visit to ensure secondary causes of hypertension would have not been identified in subsequent months.
 - In case of clinical need, and if subjects are agreeable, they will be referred to QEUH General Medicine/Hypertension Clinic, led by NHSGGC [name]/[name] for further diagnosis and treatment..

4.4 Study Schedule and Trial Procedures

Table 1: Schedule of InflammaTENSION Study procedures

Study Procedure	Baseline Visit 0 at CRF	Visit 1 at CRF	Telephone visit/Letter Drop
Timeframe	V0	V0+(0-72h)	V1+12m±2w
Demographic History	X	-	X
Medical History	X	-	X
Height and Weight	X	-	X
Urine Sample	X	-	-
Heart Rate	X	-	-
Office Blood Pressure measurement – 3 times following 15 minutes of rest	X	-	-
Venous Blood Sample (40ml) for Blood Tests and Immune signature/Biomarker analysis	X	-	-
Venous Blood Sample (10ml) for storage for subsequent genetic analysis	X	-	-
Ambulatory Blood Pressure Monitor Installation if no ABPM performed within past 3 months	X	-	-
MCQ	-	X	-
MoCA	-	X	-
DSS	-	X	-
IDQ	-	X	-
IPAQ	-	X	-
ABPM monitor will be returned	-	X	-
Carotid Intima-Media Thickness	-	X	-
Flow Mediated Dilation of Brachial Artery	-	X	-
Endo-PAT2000	-	X	-
Sphygmocor study	-	X	-

Key	- Not performed	X Performed
-----	-----------------	-------------

h hours

w – weeks

m - months

General Considerations

In hypertensive subjects' study visit(s) will be arranged as soon as possible after initial diagnosis of hypertension and before initiation of the treatment for hypertension. The study visit will not delay initiation of therapy in any way and will be fitted in between the hypertension work-up and subsequent clinic visit. In subjects recruited from GHBPC (QEUEH) this will be organized following initial diagnostic ABPM which is routinely performed prior to patient being seen by a consultant. In patients recruited from elsewhere – this will be arranged as soon as possible after identification and GP will be informed about ABPM which will be performed as part of the study by a letter from InflammaTENSION clinical team member.

Secondary hypertension will be excluded as per routine clinical practice. We also planned a letter drop questionnaire or telephone visit/data review 3-4 months after initial visit in order to verify secondary/primary status of hypertension. While we have planned baseline visit and Visit 1 separately with ABPM being performed in between, subjects who do not require ABPM (it is available within past 3 months) we will offer an option to combine these visits in one day for the patients.

Baseline Visit (Visit 0)

Meeting: The InflammaTENSION investigators will meet the participants at reception of the CRF.

Estimated Duration of Baseline Visit: Approximately 0.5 - 1 hours

Recording of Study Information: The data from the study procedures will be recorded in the electronic case report form (e.g. CASTOR EDC).

Study Procedures Performed at the Baseline Visit will include:

(Please refer to the InflammaTENSION Study Manual of Procedures for more details relating to the study procedures)

- Demographic History
- Medical History
- Height and Weight
- Urine Sample
- Office Blood Pressure measurement – 3 times following 5 minutes of rest
- Venous Blood Sample (40ml) for Blood Tests and Immune signature/Biomarker analysis
- Venous Blood Sample (10ml) for storage for subsequent genetic analysis
- Ambulatory Blood Pressure Monitor Installation if no ABPM performed within past 3 months
- Subjects will be given an IDQ questionnaire (The Interheart Diet Questionnaire) to be returned during visit 1

All procedures will be performed in both Cases and Control groups including ABPM as it will ensure that hypertension is not missed by office blood pressure readings.

Anonymisation

- Patient data will be pseudo-anonymised with a study number given to the patient. This study number will be used for blood tubes. The study specific number will be used for all storage of electronic and paper data relating to the:
 - Vascular function determinations
 - Immune signature determinations (cytokine/chemokine and cellular)
 - Cognitive function questionnaires
 - Will be blinded towards hypertension status and group allocation.
- Only the Chief Investigator, and designated and trained research fellow, who is a member of the direct care team, will have access to the participants' personal data during the study. These procedures will comply with the 1998 Data Protection Act. Biological samples collected from participants as part of this study will be transported, stored, accessed and processed in accordance with national legislation relating to the use and storage of human tissue for research purposes and such activities will meet the requirements as set out in the 2004 Human Tissue Act and the 2006 Human Tissue (Scotland) Act.

Visit 1 (CRF)

Study Procedures performed at Visit 1 at CRF (either in combination with baseline or up to 72h after baseline Visit)

NB: There is no need for a study specific ABPM if a routine care ABPM has been performed within the past 3 months.

This visit will take approximately 2-3.5 the following study procedures will be performed at the final visit.

- Questionnaires
 - ✓ MCQ The Mild Cognitive Impairment Questionnaire
 - ✓ MoCA Montreal Cognitive Assessment
 - ✓ DSS Digital Symbol Substitution
 - ✓ IDQ The Interheart Diet Questionnaire
 - ✓ IPAQ The International Physical Activity Questionnaire
- ABPM monitor will be returned
- Carotid Intima-Media Thickness
- Flow Mediated Dilation of Brachial Artery
- Endo-PAT2000
- Sphygmocor study

Participants will be thanked for taking part in the InflammaTENSION study.

Letter drop / Telephone contact (3.5 months +/- 14days)

A follow - up letter will be sent by post or e-mail to all participants asking for filling in a questionnaire regarding the key changes in medical status since Visit 0. It will also announce possible telephone contact if no response is received to initial letter

The telephone registration process will include:

- Obtaining information on participant health status changes; changes in demographics; changes in medical history and in particular verification if any cause for secondary hypertension has been identified.

4.5 Study Outcome Measures

4.5.1 Primary Outcome Measure

Cytokine and cellular immune signature of primary hypertension.

Association between hypertensive status assessed by ABPM and immune signature analysed as a whole as well as individual pro- and anti- inflammatory cytokine levels and discreet immune cell populations.

4.5.2 Secondary Outcome Measure

- Association of selected cytokine/chemokine levels with vascular phenotypes
 - endothelial function assessed by Endo-PAT2000, a non-invasive technique.
 - Large vessel endothelial function assessed by brachial artery flow mediated dilatation, a non-invasive technique.
 - Changes in cardiovascular parameters through non-invasive hemodynamic measurements
- Association of selected cytokine/chemokine levels with renal phenotypes
 - GFR; renin levels; aldosterone levels
- Association of selected cytokine/chemokine levels with cognitive dysfunction
 - Results of MCQ, MoCA, DDS
- Association of selected cytokine/chemokine levels with genetic variation assessed by GWAS

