our insufficient understanding of the underlying mechanisms of this disease. While some cases of hypertension are due to single gene mutations⁶, or underlying correctable causes such as renal artery stenosis, pheochromocytoma or adrenal adenoma⁷, these are uncommon and the cause of the majority of cases of adult hypertension are unknown. In these cases, neurohumoral factors such as angiotensin II play key roles, as drugs interfering with this pathway are anti-hypertensive. Systemic vascular resistance is generally elevated in hypertension⁸⁻¹⁰, and vasodilators lower blood pressure, which would suggest that hypertension, is a *vascular disease*. In contrast, the genetic disorders causing hypertension often affect sodium transport in the distal nephron⁶. Therefore we would like to assess genetic difference in cytokine and chemokines in the study cases and controls. Transplant of kidneys lacking the angiotensin II AT1a receptor into wild-type mice causes resistance to angiotensin II-induced hypertension¹¹ and diuretics are effective anti-hypertensive agents¹², which in turn suggests that *the kidney* is a major cause of high blood pressure. Finally, there is ample evidence that the *central nervous system*, and in particular the circumventricular organs surrounding the third ventricle, play a critical role in hypertension¹³. These seemingly disparate roles of the vasculature, the kidney and the CNS make the aetiology of hypertension very difficult to comprehend. Importantly, we have made an observation that helps link the vasculature, the kidney and the CNS in the genesis of hypertension, as all appear to be related to a common inflammatory mechanism. These studies have initiated a new research area, which over the past few years has led to the better understanding of inflammation in hypertension.

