1.4 Study hypothesis

We hypothesize that primary hypertension is associated with distinct pattern of changes within immune/inflammatory systems consisting of cytokines/chemokines and individual immune cell populations and that this immune signature corresponds with vascular, renal or cognitive phenotypes of hypertension.

2. Study Objectives

The InflammaTENSION pilot study is an observational study aiming to define the cytokine and cellular immune signature of primary hypertension.

- **Primary Endpoint**

Cytokine and cellular immune signature of primary hypertension

- **Secondary Endpoints**

1. Relationships and predictive value of the immune signature of hypertension and clinical phenotypes of hypertension

- Predictive value of immune signature for blood pressure parameters measured by ambulatory blood pressure measurements (ABPM)
- Predictive value of immune signature for endothelial function assessed by Endo-PAT2000 and flow mediated dilatation (FMD) both complementary non-invasive techniques.
- Predictive value of immune signature for vascular stiffness and central pressure assessed by Sphygmocor
- Predictive value of immune signature for renal function parameters
- Predictive value of immune signature for cognitive function

2. To define genetic determinants of immune signature of hypertension which could be used for future mendelian randomization studies.

3. Study Design

The InflammaTENSION study will be performed according to the Research Governance Framework for Health and Community Care (Second edition, 2006).

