6.2 Sample Size

The sample size will comprise of 120 participants per study arm (120 cases + 120 controls).

Based on preliminary data: at least 116 subjects will allow us to detect an IL-6 difference of 25% at a two-sided alpha of 0.1% and power of 90% (multiple markers were tested, giving similar or smaller group; TNF- α – 58 subjects). 87 subjects/group for a 25% difference in CD8+CD25+ T cell ($\alpha=0.1\%$, power - 90%). These analyses take into account multiple comparisons which are foreseen for immune signature determination.

We believe that these projected effect sizes would potentially be clinically meaningful and credible.

7. Study Closure or Definition of End of Trial

The study will end when:

- Final participants attend last study visit

OR

- i. The planned sample size has been achieved;
- ii. There is insufficient funding to support further recruitment, and no reasonable prospect of additional support being obtained;
- iii. Recruitment is so poor that completion of the trial cannot reasonably be anticipated.

8. Data Handling

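### The genetic secondary outcome is a genome-wide scan in 240 people with no power or error-control provision; a first-tier test at each marker's own gene would use the same genotypes better

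*Combined protocol and SAP*

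**What the plan says.** Section 4.5.2 lists as its last secondary outcome "Association of selected cytokine/chemokine levels with genetic variation assessed by GWAS". Section 2 (Study Objectives, secondary endpoints) gives the purpose: "To define genetic determinants of immune signature of hypertension which could be used for future mendelian randomization studies". Section 1.1 adds a related interest: "Therefore we would like to assess genetic difference in cytokine and chemokines in the study cases and controls". The material is a baseline blood sample, listed in section 4.4 as "Venous Blood Sample (10ml) for storage for subsequent genetic analysis".

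Section 6.2 plans 120 cases and 120 controls. Section 3.5 keeps that number by replacement: "Participants who withdraw from the study will be replaced with additional participants until 120 participants/arm have attended the final study visit". The power statement in section 6.2 covers IL-6, TNF-alpha and CD8+CD25+ T cells, and its multiplicity allowance is for the immune signature. No section gives a genome-wide threshold, a genetic model, covariates, the list of selected markers, a replication sample or a detectable genetic effect. Section 6.1 promises a separate comprehensive SAP but does not mention the genetic analysis when describing it.

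**The concern.** A genome-wide scan pays a very heavy multiplicity price, and 240 people is a small sample to pay it with. A null result would say little about whether genetic determinants exist. A positive result would tend to overstate the variant's effect, because only large observed effects can cross the threshold. Either result could mislead later Mendelian-randomization work if it were taken at face value. The measured proteins each have a known gene, so a much smaller set of tests is available on the same genotypes, and the plan does not use it.

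**Working it through.** **Inputs from the documents.** N = 120 + 120 = 240 (section 6.2; withdrawals replaced, section 3.5). The two protein panels in section 1.2 have 45 and 92 targets, so 137 if overlap is ignored.

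**Assumptions, not in the documents.** Threshold 5e-8 per marker; 80% power (range 50% to 90%); additive one-degree-of-freedom test; cases and controls pooled; 100 to 200 effective tests per gene region; Bonferroni correction.

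**The plan's own figure.** There is none for genetics. The 116 subjects for IL-6 in section 6.2 cannot be confirmed because no SD is given. Read as per group, (3.291 + 1.282)^2 = 20.90, so d = sqrt(2 x 20.90/116) = 0.60, which implies SD/mean = 0.25/0.60 = 0.416. That is a two-group comparison at alpha 0.1% and has no bearing on the scan.

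**Step 1: effect detectable with 80% power.** k = (z for 1 - alpha/2, plus z for power)^2 and r2 = k/(N + k). The exact version uses the noncentral F with 1 and 238 degrees of freedom and noncentrality N r2/(1 - r2).

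- Scan at 5e-8: k = (5.451 + 0.842)^2 = 39.60; r2 = 39.60/279.60 = 14.2%; exact F 15.0%.
- Same scan at 50% power: 11.0-11.7%. At 90% power: 15.9-16.8%.
- Corrected for 45 markers (alpha 1.1e-9): k = 48.08; r2 = 48.08/288.08 = 16.7%; exact F 17.8%. For 137 markers: 17.4-18.6%.
- One arm only (N = 120), at 5e-8: 39.60/159.60 = 24.8%; exact F 27.3%.
- Sample needed at 5e-8, N = k(1 - r2)/r2: 39.60 x 9 = 356 at r2 = 10%; 39.60 x 19 = 752 at 5%.

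**Step 2: power at N = 240, exact F.** Own-gene alpha is 0.05/(45 x 100) = 1.1e-5 or 0.05/(45 x 200) = 5.6e-6.

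| True r2 | Scan, one marker (5e-8) | Scan, 45 markers | Own gene, 45 x 100 | Own gene, 45 x 200 |
|---|---|---|---|---|
| 2% | 0.05% | <0.1% | 1.3% | 0.9% |
| 3% | 0.2% | <0.1% | 4% | 3% |
| 5% | 2.2% | 0.4% | 18% | 14% |
| 10% | 33% | 13% | 75% | 69% |
| 15% | 80% | 56% | 98% | 97% |

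The like-for-like comparison is between the last three columns, which all correct for 45 markers.

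**Step 3: smallest observed r2 that can be significant.** This is c/(238 + c), where c is the critical value.

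- Scan at 5e-8: chi-square 29.72/267.72 = 11.1%; F 31.72/269.72 = 11.8%. A true 3% variant that crosses is overstated at least 11.1/3 = 3.7-fold.
- Own gene: F 20.16/258.16 = 7.8% (100 tests) or 21.60/259.60 = 8.3% (200 tests). A true 3% variant is still overstated about 8.3/3 = 2.8-fold at 200 tests.

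**Step 4: how far the gain depends on the set of tests.** The r2 detectable at 80% power (exact F) is 10.6% for 45 markers x 100 tests and 11.5% for 137 x 100. If each of 45 markers were tested against all 45 loci it would be 13.7%, and most of the gain would be gone. With 137 markers x 200 tests, own-gene power at r2 = 10% is 61%. One pre-named variant per protein (alpha 0.05/45 = 1.1e-3) would give 97% at r2 = 10% and 60% at 5%, but the documents name no such variants.

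**The case against.** The strongest case against the point is that this is an exploratory secondary outcome that is merely under-specified. Section 2 calls the study a pilot, section 6.1 defers detail to a later SAP, and the blood is only being stored. Section 4.5.2 speaks of selected markers, so correction for 45 or 137 is assumed. All of this is true, and it lowers the weight of the point. It does not remove it: section 4.5.2 already fixes the method as a genome-wide scan, and 240 people is a limit that no later SAP can lift.

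It can also be said that the own-gene test changes the question. It gives up discovery elsewhere in the genome and has no counterpart for immune cell populations, which belong to the immune signature. It is weak at r2 of 2-5% and still inflates hits. These limits are real, which is why the scan should stay as a second tier rather than be dropped.

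Several stronger readings are tempting, and the documents do not support them:

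- A reader might take 14% as a floor on what can be found. It is the effect with 80% power; a 10% variant is found about one time in three.
- A reader might conclude that the scan cannot supply instruments. The documents give no genetic effect sizes, so large effects are not excluded.
- A reader might say that the plan promises instruments. Section 2 says only that the determinants could be used in future studies, and nothing says that hits would be used without replication.
- A reader might cite section 1.1 as already calling for an own-gene analysis. It describes a comparison between cases and controls, which is a different test.

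**Conclusion.** The point holds as a worthwhile improvement to a secondary outcome; the primary endpoint is not affected. As written, the scan has 80% power only for variants explaining about 14-15% of a marker's variance, or about 17-18% after correction for 45 markers, and its hits will be inflated when the true effect is smaller than about 11-12%. It is therefore unlikely to give usable determinants unless effects are large. An own-gene first tier raises power at r2 = 10% from 13% to about 69-75% at the same marker correction. It improves the odds for effects of roughly 5-10%; it does not secure instruments, and at 2% it has about 1% power. These figures rest on the assumed 5e-8 threshold, pooling of all 240, 45 markers, and 100 to 200 effective tests per gene region.

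**What to change.** In section 4.5.2, replace the last bullet with two tiers, and carry them into the SAP before any genotypes are analysed.

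1. **First tier.** List the selected cytokines and chemokines. Test each one's level only against variants in and around its own gene, with the region and the number of effective tests defined in advance and error control across all these tests. Model the log marker level, adjusted for age, sex, BMI, case status and ancestry components.
2. **Second tier.** Keep the genome-wide scan, labelled exploratory, with its threshold, number of markers and detectable r2 stated.
3. **Use of results.** In section 2, limit any Mendelian-randomization use to loci replicated in an outside sample, and report that effect sizes at significant loci are likely to be overestimated.

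The cost is protocol and SAP wording; the DNA and genotypes are the same. The downside is that confirmatory claims are limited to own-gene loci. Findings elsewhere in the genome, and any genetic findings for immune cell populations, stay exploratory. If the case-control interest in section 1.1 is to be tested, it needs its own statement, because the model above adjusts for case status.

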4.6. Incidental findings

Any incidental findings observed during the research procedures will be acted upon: this means that the PI takes responsibility to notify the patients GP and refer on for specialist follow up as appropriate and with the patient or participants permission.

Patients who would benefit from hypertension/cardiovascular risk factor management will be referred to and provided with contact details for NHSGGC [name]/[name] led clinic *at the QEUH General Medicine/Hypertension Clinic for further diagnosis and treatment.*

6. Statistics and Data Analysis Plan

6.1 Statistical Analysis Plan

The InflammaTENSION study will have a comprehensive Statistical Analysis Plan, which will govern all statistical aspects of the study, and will be authored by the Study Statistician ([name]). To gain additional insight, variable selection analysis will be used to identify the best predictors of hypertension and its vascular outcomes (endothelial function/vascular compliance). To do this we will draw the expertise of local bioinformaticians ([name]) and of [name], a theoretical immunologist at University of Glasgow with experience in the modeling of cytokine networks and in machine learning approaches to TCR repertoire analysis. We anticipate using exploratory unsupervised approaches such as Principle Component Analysis and clustering may be used on the cytokine profiles to identify signature patterns of cytokine expression that may allow a reduction of dimensionality. One can also associate each patient's cytokine profile with a score - either one dimensional measure of disease severity or perhaps multi-factorial measures, combining severity with demographic data, for example, and use supervised learning approaches such as support vector machines or neural networks to generate classifiers or predictors of outcomes.

